6.3.5 Laboratory Evaluations

Sites must refer to the DAIDS Table for Grading the Severity of Adult and Pediatric Adverse Events (DAIDS AE Grading Table), Version 2.0, November 2014, which can be found at <http://rsc.tech-res.com/safetyandpharmacovigilance/gradingtables.aspx>.

Record all protocol-required laboratory values, regardless of grade, obtained at screening and entry on the CRFs.

After entry, record all laboratory values Grade ≥ 2 . Record all lipid values (Total, HDL, and LDL cholesterol, triglycerides) regardless of grade on the CRF. All laboratory values that lead to a change in study treatment, and all serum creatinine and liver function tests (AST, ALT, alkaline phosphatase, total bilirubin) regardless of grade, must be recorded.

Hematology

Hemoglobin, hematocrit, white blood cell count (WBC), with differential, absolute neutrophil count (ANC), and platelet count.

Liver Function Tests

AST (SGOT), ALT (SGPT), alkaline phosphatase, total and direct bilirubin

Blood Chemistries

sodium, potassium, chloride, bicarbonate, random glucose, BUN, creatinine, aspartate aminotransferase (AST/SGOT), alanine aminotransferase (ALT/SGPT), alkaline phosphatase, total bilirubin, direct bilirubin, total protein, and albumin.

Fasting Lipids

Total, HDL, and LDL cholesterol, triglycerides.

If triglycerides are >400 at screening and/or high enough that LDL can't be calculated, then come back for direct LDL. Subsequent LDL should be direct in those patients.

Subjects should be instructed to fast for 8 hours prior to this test. Fasting is defined as no food or drink, except for sips of water with medications. If the subject has not been fasting, the visit must be rescheduled. Record the non-fasting status on the CRF.

Pregnancy Test

All women with reproductive potential must have a negative serum or urine beta-human chorionic gonadotropin (β -HCG) pregnancy test result at screening and within 48 hours prior to initiating protocol-specified medications and any time thereafter when pregnancy is suspected. (The urine test must have a sensitivity ≤ 50 mIU/mL).

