7.0 CLINICAL MANAGEMENT ISSUES

7.1 Toxicity Management

Criteria for subject management, dose interruptions, modifications, and discontinuation of study treatment will be mandated only for toxicities attributable to study-provided drugs (pravastatin and rosuvastatin).

The grading system for drug toxicities is the DAIDS Table for Grading the Severity of Adult and Pediatric Adverse Events, Version 2.0, November 2014, located at <http://rsc.tech-res.com/safetyandpharmacovigilance/gradingtables.aspx>.

The lone difference between the grading system for drug toxicities used in this trial and the DAIDS Table is that our protocol has a lower threshold for grading transaminase (AST and ALT) elevations; based on the current ACC/AHA and National Lipid Association Guidelines, we consider elevation of AST or ALT ≥ 3 x ULN as grounds for holding the study drug (and a grade 3 adverse event in this protocol), and CK ≥ 10 x ULN as a grade 3 adverse event and grounds for holding the study drug.

NOTE: The HILLCLIMBER protocol chair must be notified by e-mail regarding toxicities that result in regimen interruption or discontinuation. Email: [contact]. General guidelines presented in sections 7.1.1 to 7.1.3 apply to toxicities that are not specifically discussed further below.

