9.2 Endpoints

9.2.1 Primary Endpoints:

Efficacy: The primary efficacy endpoint is mean percent change in fasting LDL-c (mg/dl) from week 2 (end of run-in period) to week 14

- The mean percent change in fasting LDL-c from week 2 to week 14 will be compared for the high dose group (rosuvastatin 20mg daily uptitrated to 40mg daily) and the moderate dose group (pravastatin 40mg daily).

Safety:

- All treatment-emergent adverse events, including but not limited to:
 - Incidence of adverse event-related study drug discontinuation (following initial 2 week wash-in) or hospitalizations
 - Grade 3 or greater adverse events;
 - Study drug-related symptoms
 - CK elevation > 3x upper limit of normal;
 - AST or ALT elevation >3x upper limit of normal;

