9.4 Sample size and Accrual

The predicted percent reduction in LDL-c by rosuvastatin dose is as follows: 20mg (55-60%), and 40mg (60-63%). The predicted percent reduction in LDL-c by pravastatin 40mg is 30%. The expected difference in LDL-c for subjects receiving high (rosuvastatin 20-40mg daily) versus moderate (pravastatin 40mg daily) intensity statin doses in this study is therefore approximately 25-30% compared with moderate. In a landmark study of patients with CHD comparing high intensity statin (atorvastatin 80mg, which is similar in intensity of expected lipid lowering to rosuvastatin 20-40mg) versus pravastatin 40mg, mean LDL cholesterol levels during treatment were 62mg/dl and 95mg/dl for high intensity and pravastatin groups (with standard deviations of approximately 20mg/dl), respectively.

Given potentially lower baseline LDL cholesterol levels in this study (we expect mean LDL of participants will be approximately 105, including patients off statin therapy and those on low intensity therapy), realistic expected mean LDL cholesterol levels are 75mg/dl for the pravastatin group and 50mg/dl for the high-intensity/rosuvastatin group. These expected LDL cholesterol levels are similar to those seen in the high intensity versus lower intensity treatment groups in a more recent trial of lipid-lowering strategies in high-risk patients, in which there was no excess of adverse events in the higher-intensity group which achieved a mean LDL of 53.7mg. In order to have a power of 0.80 with a two-sided alpha of 0.05 to detect a 25mg/dl difference in LDL-c lowering with a standard deviation of LDL-c of 20, the desired sample size would be at least 11 cases and 11 controls. Given the potential for study drug discontinuation in an expected 8 or fewer patients (based on on-treatment symptoms being present in 5-20% of patients on statins), the goal subject enrollment for this study is 30 with a possible enrollment of up to 50 participants in order to ensure adequate power.

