9.6.2 Secondary Analyses

Safety and tolerability data will be summarized by treatment group.

Adverse events (signs, symptoms, and diagnoses) will be analyzed and reported using the AIDS Clinical Trials Group (ACTG) medical dictionary and standardized coding for Signs, Symptoms, and Diagnoses for Clinical and Adverse Events. Adverse events will be tabulated by treatment group and will include the number of patients for whom the event occurred, the rate of occurrence, and the severity and relationship to study drug.

Incidence of clinical and/or laboratory toxicities. The safety and tolerability measures will include:

- Time to discontinuation of any study medication due to adverse events (AEs), --
- Proportion of Grade 3 or Grade 4 clinical AEs,
- Proportion of Grade 3 or Grade 4 laboratory abnormalities,
- Summaries of all treatment-related AEs

Possible future analyses

- Measures of the HIV reservoir size
- Soluble and cellular markers of immune activation and inflammation

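### Every named CK, AST and ALT safety measure is a threshold count; add a log-scale between-arm estimate beside the counts, and record CK at all grades

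*Combined protocol and SAP*

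**What the plan says.** Section 9.2.1 lists, among the safety endpoints, "CK elevation > 3x upper limit of normal" and "AST or ALT elevation >3x upper limit of normal". The list is expressly open-ended. Section 9.6.2 has safety data summarised by arm, and its only named laboratory measure is "Proportion of Grade 3 or Grade 4 laboratory abnormalities". It names no test.

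The schedule in 6.1 has liver tests and CK at screening and at weeks 0, 2, 6, 10 and 14 in both arms. Section 9.2.2 analyses change from week 2 to week 14 for lipids, biomarkers and haemoglobin A1c, but not for CK, AST or ALT.

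Under 6.3.5, laboratory values after entry go on the CRF from Grade 2 upward or if they change treatment. There is an exception: "all serum creatinine and liver function tests (AST, ALT, alkaline phosphatase, total bilirubin) regardless of grade, must be recorded". CK is not in it. In the table in 7.1.3, CK Grade 1 is 3 to <6x ULN and Grade 2 starts at 6x ULN.

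Section 2.0 calls the trial a pilot and leaves adequate power for safety to future studies.

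**The concern.** A pilot should hand on an estimate. Entry excludes AST or ALT above 3x ULN, CK above 10x ULN and prior statin intolerance (4.2), so few exceedances are likely. A table of 0 or 1 in each arm would say almost nothing about whether rosuvastatin 20 to 40 mg moves CK or transaminases relative to pravastatin 40 mg. Section 2.1 says that no trial has tested those rosuvastatin doses in people with HIV on ART. The values that could inform that question are collected, but no analysis of them is named.

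The CRF rule adds a data problem. A CK of 4x ULN counts toward the endpoint, yet as a Grade 1 value it must be recorded only if it changes treatment. Entry is at week 0, so the rule also covers the week-2 CK value that would serve as baseline.

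**Working it through.** **Inputs.** Section 9.4 gives an enrolment goal of 30 and up to 50; 3.0 gives up to 40. At 1:1 allocation that is 15, 20 or 25 per arm. The "two-sided alpha of 0.05" is stated for LDL-c and borrowed here for illustration. The documents give no exceedance rate, SD or expected shift for CK, AST or ALT, so those below are assumptions. Each calculation uses one value per patient.

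**The plan's own figure.** Section 9.4 sizes the trial "to detect a 25mg/dl difference in LDL-c lowering" with SD 20 and power 0.80: n = 2 × [(1.960 + 0.842) × 20/25]² = 10.05, rounded up to 11 per arm. This matches the plan. No such calculation exists for laboratory safety.

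**What counts can show.** With 0 of n against j of n, Fisher's two-sided p = 2 × C(n, j) / C(2n, j).

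- n = 20: j = 4 gives 2 × 4845/91390 = 0.106; j = 5 gives 2 × 15504/658008 = 0.047.
- n = 15: j = 4 gives 2 × 1365/27405 = 0.0996; j = 5 gives 2 × 3003/142506 = 0.042.
- n = 25: j = 5 gives 2 × 53130/2118760 = 0.0502; j = 6 gives 0.022.

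Zero of 20 in one arm leaves an upper 95% limit (two-sided exact) of 1 − 0.025^(1/20) = 0.168, or 17%.

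**If the whole distribution shifts.** Assume normal log values with equal SD. Control rate p0 and rosuvastatin rate p1 then imply a shift d = z(1 − p0) − z(1 − p1). For 5% versus 20%, d = 1.645 − 0.842 = 0.80 SD. Fisher power sums over both binomials. The t-test uses the noncentral t with 2n − 2 degrees of freedom and noncentrality d × √(n/2).

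| Per arm | Assumed rates | Fisher on the cut | t-test on log values |
|---|---|---|---|
| 15 | 5% v 20% | 8% | 57% |
| 20 | 5% v 20% | 17% | 70% |
| 25 | 5% v 20% | 20% | 80% |
| 20 | 1% v 10% | 4% | 90% |
| 20 | 10% v 20% | 7% | 27% |
| 20 | 5% v 10% | 2% | 20% |

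Adjusting for week 2 at an assumed correlation of 0.5 raises the effective d to 0.80/√(1 − 0.25) = 0.93 SD, and the 70% to about 82%.

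**If only a subgroup is affected.** Simulation at 20 per arm, control rate 5%, with a fraction of rosuvastatin patients set to at least 0.3 SD above the cut:

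- 15% affected (exceedance 0.15 + 0.85 × 0.05 = 19%): Fisher about 15%, t-test about 13%.
- 30% affected (0.30 + 0.70 × 0.05 = 34%): Fisher about 54 to 55%, t-test about 37%.

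The gain disappears in the first case and reverses in the second.

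**Precision of the added estimate.** Without adjustment, the 95% half-width for the difference in log means is t × √(2/n). At 20 per arm it is 2.024 × 0.316 = 0.64 SD; at 15, 0.75 SD; at 25, 0.57 SD. The estimate is usable but not tight.

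**The case against.** A reader might infer that the trial will test safety through these cuts, almost always miss a real rosuvastatin effect, and report no difference. The documents do not support that. Section 9.6.2 plans summaries by arm with no test, and 2.0 defers safety power to later studies. Section 9.2.1 does list safety under primary endpoints, while 1.2, 9.2.2 and 9.6.2 treat it as secondary; that is a separate inconsistency and does not create a test. Nor does "almost always" follow from the numbers: at 20 per arm and a 1 SD shift, the cut has power 0.03 to 0.11 at control rates of 1 to 2%, but 0.33 to 0.46 at 5 to 10%. A 0.5 SD shift would usually be missed on either scale (t-test power 0.26, 0.34 and 0.41 at 15, 20 and 25 per arm).

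A reader might also infer that the 3x CK cut has no basis, because 7.1 cites guidelines only for AST/ALT at 3x ULN and for "CK ≥ 10 x ULN as a grade 3 adverse event and grounds for holding the study drug". But 3x ULN is the protocol's own CK Grade 1 boundary (7.1.3), a week-6 escalation criterion (5.1) and the monitoring level in 9.5. Counting patients who reach it is reasonable.

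The open-ended list would permit a continuous summary, and AST and ALT are already recorded at all grades. What stands is that none is specified and that CK may be incomplete. How incomplete depends on which rule is followed. Under 9.5, CK at 3x ULN or more stops the drug, so the value would be recorded; 5.1 and 7.1 do not stop it at that level. Those passages need reconciling in their own right. Until then, capture of CK at 3 to <6x ULN is uncertain, and could differ by arm because week-6 CK decides escalation only on rosuvastatin.

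**Conclusion.** The point holds as a gap in estimation. All named CK, AST and ALT safety measures are thresholds, and at 15 to 25 per arm their counts give later studies little between-arm information. The possible gain from using the values is large under a common shift (17% to 70% power in the central example) and nil or negative under subgroup toxicity. The documents give nothing to choose between these, so the log-scale estimate belongs beside the counts and cannot replace them. The CK recording gap in 6.3.5 rests on no distributional assumption and affects the existing endpoint as well as the proposed summary.

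**What to change.** In 9.6.2, keep the threshold and Grade 3/4 counts. Add, for CK/ULN, ALT/ULN and AST/ULN, the between-arm ratio of geometric means with 95% confidence interval at weeks 6, 10 and 14, from a repeated-measures model of log values adjusted for the week-2 log value, in all randomised patients. Label it as estimation, not a powered test. State that values taken after drug is held or escalation is withheld are included and pull the estimate toward no difference.

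In 6.3.5, require CK at every grade on the CRF after entry, as for AST and ALT. Leave all dose and stopping thresholds unchanged.

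The cost is a few sentences, one model per analyte and slightly more data entry, with no new visits or draws. The downside is that a shift in geometric mean is not itself a clinical event, so it must always be reported next to the counts.

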9.2.2 Secondary Endpoints

Secondary endpoints include mean percent changes in the following from week 2 to week 14:

- Lipid parameters (HDL-c, triglycerides, and total cholesterol),
- Inflammatory biomarkers (soluble CD163, ST2, high sensitivity troponin I, high-sensitivity CRP, PAI-1, Lp-PLA2)
- Viral and immunologic markers derived from PBMCs (such as T cell reactivity and viral reservoir persistence).
- Statin drug levels >400% expected steady-state dose level
- Hemoglobin A1c level

An additional secondary endpoint will evaluate safety, as measured by treatment-

emergent clinical and laboratory adverse events, of high versus moderate intensity statin therapy in HIV-infected persons taking ART who have coronary heart disease (CHD) and/or 15% or greater risk for ASCVD.

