6.0 CLINICAL AND LABORATORY EVALUATIONS

6.1 Schedule of Events

	SCREEN- ING	WEEK 0 ^a	WEEK 2 ^a	WEEK 6 ^a	WEEK 10	Week 14/ or discontinuation
Informed Consent	X	X				
Medical and Medication History (including cardiovascular risk; HIV RNA and CD4, lipids)	X					
Complete Physical Exam	X					
Targeted Physical Exam		X	X	X	X	X
Height , Weight	X				X	
Vital Signs	X	X	X	X	X	X
Chemistry Panel, Liver Function Tests	X	X	X	X	X	X
Creatine Kinase	X	X	X	X	X	X
Fasting Lipid Panel	X	X	X	X	X	X
Pregnancy Test	X	X				X
Hematology, Hemoglobin A1c		X				X
Stored Plasma/Serum/PBMCs		X	X			X
Pharmacokinetics/dynamics			X	X		X
Randomization			X			
Dispensing of Study Drug		X	X	X	(X)*	
Adherence Assessment			X	X	X	X
Concomitant Medication Review	X	X	X	X	X	X
AE Determination		X	X	X	X	X
Phone Call					(X)*	
Statin Intolerance Survey			X	X	X	X

*(X) if on escalated rosuvastatin dose (40mg daily)

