6.3 Instructions for Evaluations

All clinical and laboratory information required by this protocol must be present in the source documents.

All stated evaluations are to be recorded on the CRF and keyed into the REDCap database unless otherwise specified.

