6.3.6 Laboratory Results from Clinical Care

CD4 count and HIV-1 RNA results will be obtained from routine clinical care and available in the EMR.

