6.3.8 Storage of PBMCs, Plasma and Serum for future studies

Virologic and Immunologic Studies:

40 mL of blood will be collected in EDTA tubes. Peripheral blood mononuclear cells (viable PBMCs) and plasma will be processed or stored for possible later analyses of cell-associated HIV RNA and DNA and T cell subsets, soluble and cellular markers of immune activation.

5 mL of blood will be collected in SST tubes and 3 mL in sodium citrate tubes and stored for later analyses of inflammatory biomarkers.

Pharmacology:

5 mL of blood for determination of plasma concentrations of pravastatin and rosuvastatin will be collected approximately 12 hours after dosing at weeks 2, 6, and 14. Participants will be instructed to take their study medications in the evening, about 12 hours before their clinic visit. Time of last dose and blood draw will be collected.

The samples will be processed and cryopreserved at the study repository at the Lurie Special Infectious Diseases (SID) Laboratory

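### HbA1c is defined as a change from week 2 but is not measured at week 2; separately, capture of CK between 3 and 6 times ULN is not assured

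*Combined protocol and SAP*

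**What the plan says.** **HbA1c.** Section 9.2.2 begins its list with "Secondary endpoints include mean percent changes in the following from week 2 to week 14". Five items follow: lipid parameters, inflammatory biomarkers, viral and immunologic markers, statin drug levels, and HbA1c. In section 6.1 the row "Hematology, Hemoglobin A1c" is marked at week 0 and at week 14 (or discontinuation) only.

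Two other sections might have supplied a week-2 value. On stored samples, section 6.3.8 says "Peripheral blood mononuclear cells (viable PBMCs) and plasma will be processed or stored", and it adds tubes kept for inflammatory biomarkers. On data from clinical care, section 6.3.6 says "CD4 count and HIV-1 RNA results will be obtained from routine clinical care", and it names no other test.

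**CK.** Section 9.2.1 lists CK above 3 times ULN among the safety endpoints. The general rule in section 6.3 is "All stated evaluations are to be recorded on the CRF and keyed into the REDCap database unless otherwise specified". Section 6.3.5 then sets a narrower rule for laboratory values. It opens with "After entry, record all laboratory values Grade", and the lowest grade that it covers is Grade 2. Lipids are entered whatever their grade. Creatinine and the liver tests are handled in the same way: "all serum creatinine and liver function tests (AST, ALT, alkaline phosphatase, total bilirubin) regardless of grade, must be recorded". A separate clause covers results that alter dosing: "All laboratory values that lead to a change in study treatment". CK is not on the any-grade list. Section 7.1.3 grades CK of 3 to below 6 times ULN as Grade 1.

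**The concern.** A percent change needs a baseline value, and the baseline named for HbA1c is never measured. Whoever runs the analysis must either move the baseline to week 0 or drop the endpoint. If this is left until the data are in hand, it becomes an undocumented post hoc choice, although a sound answer is available now.

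For CK, the endpoint threshold lies below the grade at which a laboratory value must be entered. A count of CK above 3 times ULN taken from the laboratory fields could therefore miss values below 6 times ULN. The parallel endpoint, AST or ALT above 3 times ULN, has no such gap, which suggests that CK was left off the list by oversight.

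**Working it through.** No sample-size or power figure is involved. The check compares each endpoint definition with the data the plan collects.

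**1. HbA1c against the schedule.** As defined, the endpoint is

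percent change = 100 × (HbA1c at week 14 − HbA1c at week 2) / HbA1c at week 2.

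Section 6.1 has six visit columns: screening and weeks 0, 2, 6, 10 and 14. The relevant rows are:

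| Item in 9.2.2 | Row in 6.1 that serves it | Visits | Week-2 sample |
|---|---|---|---|
| Lipids | Fasting lipid panel | all six | yes |
| Inflammatory biomarkers | Stored plasma/serum | 0, 2, 14 | yes |
| Viral and immunologic markers | Stored PBMCs | 0, 2, 14 | yes |
| Statin levels | Pharmacokinetics | 2, 6, 14 | yes |
| HbA1c | Hematology/HbA1c | 0, 14 | no |

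HbA1c is drawn at 2 of 6 visits, and 4 of the 5 items have a scheduled week-2 sample. The column alignment can be trusted: section 6.3.8 independently gives weeks 2, 6 and 14 for drug levels, matching the pharmacokinetics row. The text of footnote *a* on the week 0, 2 and 6 headings is not in the extracted table. It is attached to those headings, not to the HbA1c row.

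The stored material is PBMCs, plasma and serum. Neither stored whole blood nor an HbA1c assay on stored samples is described. The formula therefore has no week-2 term.

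**2. CK grades against the recording rule.** Applying the grades in section 7.1.3:

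| CK (× ULN) | Grade | Meets endpoint (>3) | Required by the Grade 2+ rule | In the Grade 3/4 measure of 9.6.2 |
|---|---|---|---|---|
| 3.1 | 1 | yes | no | no |
| 4 | 1 | yes | no | no |
| 5.9 | 1 | yes | no | no |
| 6 | 2 | yes | yes | no |
| 9.9 | 2 | yes | yes | no |
| 10 | 3 | yes | yes | yes |

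The band above 3 and below 6 times ULN falls outside the grade rule. The band above 3 and below 10 falls outside the Grade 3/4 measure. AST and ALT are recorded at any grade, and section 7.1 makes 3 times ULN Grade 3.

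**3. The treatment-change clause.** It can bring a Grade 1 CK onto the CRF when the value alters treatment:

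- Section 9.5 stops drug at CK of 3 times ULN or more at weeks 2, 6 or 10.
- Section 5.1 blocks escalation at week 6 for CK of 3 to 10 times ULN, in the rosuvastatin arm only.
- Section 7.1.1, by contrast, lets Grade 1 or 2 toxicity continue on drug. If a site follows it rather than section 9.5, no treatment change occurs and entry is not forced.
- At week 14 there is no later study treatment to change, so the clause cannot apply. That is 1 of the 3 post-randomisation CK visits (weeks 6, 10 and 14). This counts visits, not lost events.

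**The case against.** The strongest reply concerns weight. HbA1c is absent from the secondary objectives in section 1.2 and is not named in the analyses in section 9.6. It appears as the last bullet of a list in a self-described pilot, and a valid pre-randomisation value exists at week 0. On this view the defect is a baseline label and no data are lost. That is fair as to size, but the stated rule still cannot be carried out.

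The list stem is also loose for another item. Statin levels are expressed as exceeding a threshold rather than as a percent change, and at week 2 every subject has taken only pravastatin. So 4 of 5 counts scheduled samples and does not show that the other four items are all well defined. That limit stands.

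On CK, the reply is that the plan has several safety nets:

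- Section 9.5 triggers a treatment change at weeks 2, 6 and 10, and an alert to the safety officer for values found before the interim analysis.
- Section 6.3.4 records Grade 1 or higher symptoms and all treatment modifications.
- Adverse events are assessed at each visit from week 0, and section 9.2.1 itself lists the CK elevation among adverse events.
- Source documents must hold every required result. With 40 subjects and 3 visits, that is at most 40 × 3 = 120 post-randomisation values to check.

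These nets narrow the gap considerably, which is why the CK point is made with moderate confidence only. None of them requires an asymptomatic week-14 CK in this band to be entered as a laboratory value.

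Finally, section 9.6.2 already promises safety summaries by group, including laboratory toxicities, so a dedicated CK row might seem a preference. But the only laboratory cut-off it specifies is Grade 3 or 4, which for CK begins well above the endpoint threshold.

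**Conclusion.** The concern holds. The HbA1c endpoint cannot be produced as written because its week-2 baseline is not measured; confidence is high. This rests on the schedule as extracted and assumes that the missing footnote does not add an HbA1c draw at week 2.

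The CK point holds in a limited form: capture of values above 3 and below 6 times ULN is not assured, most clearly at week 14. How many subjects would fall in that band cannot be derived from the documents. No bias between arms is claimed, and the primary LDL-c comparison is unaffected. Both points should be corrected before analysis, but neither threatens the trial.

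**What to change.** In section 9.2.2, define HbA1c as

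percent change = 100 × (HbA1c at week 14 − HbA1c at week 0) / HbA1c at week 0.

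Week 0 precedes randomisation. The longer window takes in the two-week pravastatin run-in, but both arms share it, so the comparison between arms remains valid. The cost is one wording change.

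The alternative is to add HbA1c to the week-2 column of section 6.1, where EDTA blood is already drawn. That keeps the endpoint as written, at the price of one extra assay per subject (40 at the planned size in the synopsis).

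For CK, add it to the tests recorded regardless of grade in section 6.3.5, as is done for AST and ALT, and add a row to section 9.6.2 for CK above 3 times ULN after week 2, by arm. CK is already measured at every visit, so this costs data entry and one table row.

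Under the preferred option no visit, draw or assay is added.
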